#### Phase 1/2/3a, Phase 2/3a, Pooled:

Since participants underwent Switchover at Day 92 or were re-randomized (participants initially randomized to ARCT-154 in Phase 2 and 3a) at Day 92 and then received Placebo at Day 120, headers by dose will be presented in the following way:

- Baseline and disposition outputs:

ARCT-154 (Initial)	Placebo (Initial)	Total
--------------------	-------------------	-------

- Analysis of data up to the Switchover/Further study vaccine:

ARCT-154 (Initial)	Placebo (Initial)
--------------------	-------------------

- Analysis of data after Switchover/Further study vaccine

ARCT-154 (Initial)	Placebo (Initial)	
ARCT-154 (Dose 3)/ Placebo (Dose 4)	Placebo (Dose 3 and 4)	ARCT-154 (Dose 3 and 4)

- Analysis of combined data before and after Switchover/Further study vaccine:

ARCT-154 (Initial)	Placebo (Initial)		
ARCT-154 (Dose 3)/	Placebo	Not Re-randomized	ARCT-154

Placebo (Dose 4)	(Dose 3 and 4)	(Dose 3 and 4)
------------------	----------------	----------------

- Analysis of data over multiple doses

ARCT-154 vaccine at any time; no ARCT-154 vaccine:

ARCT-154	Placebo
----------	---------

- Analysis of data from the first dose of ARCT-154 vaccine administration:

ARCT-154
----------

### Phase 3c

- Baseline and disposition outputs:

ARCT-154	ChAdOx1	Total
----------	---------	-------

- Other outputs:

ARCT-154	ChAdOx1
----------	---------

## 5.4 Withdrawals, Dropouts, Loss to Follow-up

Participants who discontinue from the study vaccine after randomization will not be replaced.

## 5.5 Visit Windows

Visit window from the target day is applied to the following visits (Study day) for analyses in the PP set:

- A window of  $\pm$  30 days: Study Day 92 (Switchover/Further study vaccine). As per protocol, for participants in Phase 1 and Phase 3b, the visit window at Day 92 is +30 days while for participants in Phase 2 and Phase 3a, the visit window at Day 92 is +14 days." For consistency across studies, the same time window will be applied for all studies.
- A window of  $\pm$  14 days: Study Day 394 (Final visit)
- A window of  $\pm$  7 days for other scheduled visits

Only assessments that fit within the protocol defined visit windows will be used in the analysis of efficacy and immunogenicity for PP analysis set.

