Study vaccine will be administered in an observer-blind fashion as described in Section [6.3](#). The second study vaccination of each series must be at least 28 days after the first study vaccination. For Phase 1 and 3b, the first Switchover vaccination (Day 92) must be at least 56 days (+30 days) after the second vaccination of the initial series. For Phase 2 and 3a, the 3rd vaccination with study vaccine must be at least 56 days (+30 days) after the second vaccination series.

After receipt of study vaccine in the initial series of vaccinations, the participant will remain under observation for at least 3 hours for Phase 1, and 30 minutes for Phase 3b, and until clinically stable. For Switchover vaccinations, participants in Phase 1 and Phase 3b will be observed for at least 15 minutes and until clinically stable. Participants in Phase 2 and 3a will be observed for at least 30 minutes and until clinically stable for vaccinations 1, 2, and 3 (Day 92) and for at least 15 minutes and until clinically stable for vaccination 4 (Day 120). During the post-vaccination observation period, the participant will undergo assessment of vital signs, body temperature, AEs, and concomitant medications prior to discharge from the clinic.

Should a participant experience a severe AE (including but not limited to hypersensitivity or anaphylaxis) immediately following study vaccine administration, the participant should be observed until clinically stable, and the Clinical Research Organization (CRO) Medical Monitor should be notified immediately. Additional evaluation or testing may be performed based on

discussion between the Medical Monitor and the investigator and subject to Medical Monitor approval.

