4.5.3.3 Follow-up Visit on Day 8 and 36 (Phase 1 only)

For Phase 1, follow-up visits on Day 8 and 36 must occur at least 7 days after each vaccination. Participants in Phase 1 will undergo the following: an interview for AEs, concomitant medications/vaccines, updates to medical history, COVID-19 exposures and/or symptoms, vital signs, body temperature, reminder to notify the site of unsolicited AEs and COVID-19 exposures and/or symptoms. Physical examination may be performed, if warranted, by the interview.

Blood will be drawn as outlined in Section [4.5.5.3](#).

4.5.3.4 Follow-up Visit on Day 57

The Follow-up visit on Day 57 must occur at least 28 days after the second vaccination. Participants will undergo the following: an interview for AEs, concomitant medications/vaccines, updates to medical history, COVID-19 exposures and/or symptoms, vital signs, body temperature, reminder to notify the site of unsolicited AEs and COVID-19 exposures and/or symptoms. Physical examination may be performed, if warranted, by the interview.

Blood will be drawn as outlined in Section [4.5.5.3](#).

For Phase 2, 3a, 3b and 3c participants who did not use the eDiary, paper diaries for the second vaccination will be collected.

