If vaccination is delayed for any of the reasons described above, subsequent study visits will be based on calendar days after the receipt of the study vaccine.

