- l Review of AEs will include surveillance for solicited (only after Day 92 vaccination and only for Phase 2 and 3a) and unsolicited AEs, SAEs, MAAEs, and AEs leading to discontinuation/withdrawal; Solicited AE data will be gathered by Diary for Day 1 through Day 7 for all participants after each of the initial vaccination series only; Unsolicited AE data will be gathered by interview at clinic visits and telephone contacts through Screening and 28 days after each vaccination. SAEs, MAAEs, and AEs leading to discontinuation/withdrawal will be collected at all timepoints after signing of the informed consent.
- m Only participants in Phase 2 and 3a complete a diary after vaccination on Day 92; no diary is completed after vaccination on Day 120. Participants in Phase 1 and 3b do not complete a diary after vaccination on either Day 92 or Day 120.
- n For participants in Phase 1 and Phase 3b, the visit window at Day 92 is +30 days. For participants in Phase 2 and Phase 3a, the visit window at Day 92 is +14 days.

- o Participants ineligible for additional doses (Section 5.1.5) do not have a clinic visit at Day 120 and will not have weekly telephone visits on Day 99 to Day 113 and Days 127 to Day 176 but will have monthly telephone visits instead on Days 120, 150, and 180.

DAY 92 TO END OF STUDY VISIT FOR PHASE 3C PARTICIPANTS

Visit Name	Weekly Study Call	Follow-up Visit	Weekly Study Call	Monthly Study Call	Final Visit	Unscheduled Visit ^b	ET Visit
Visit Type ^a	TC	Clinic	TC	TC	Clinic	Clinic	Clinic
Study Day:	92, 99, 106, 113, 120, 127, 134, 141, 148, 155, 162, 169, 176, 183, 190, 197, 204	211	218, 225, 232, 239, 246, 253, 260	290, 320, 350	394	N/A	N/A
Visit Window (days):	± 2	+30	± 2	± 2	+14	N/A	N/A
Physical examination ^c		X			X	X	X
Vital signs and body temperature ^d		X			X	X	X
Pulse oximetry						X	
Blood sampling ^e		X			X		X
Nasal swab sample for RT-PCR SARS-CoV-2 ^f						X	
Review of Medical History		X			X	X	X
Review for COVID-19 symptoms and risks ^g	X	X	X	X	X	X	X
Adverse events ^h	X	X	X	X	X	X	X
Concomitant medication/vaccines collection	X	X	X	X	X	X	X

Abbreviations: AE=adverse event; COVID-19=coronavirus disease 2019; ET=early termination; MAAE=medically attended adverse event; N/A=not applicable; RT-PCR=reverse transcription polymerase chain reaction; SAE=serious adverse event; SARS-CoV-2=severe acute respiratory syndrome coronavirus 2; TC=telephone call

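### SAP 5.5 calls its symmetric per-protocol windows protocol defined although the protocol's are one-sided: an early Day 57 draw passes and, if days run from Day 1, some on-schedule Day 120 samples drop out

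*SAP*

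**What the plan says.** SAP 5.5 gives three windows for PP analyses, each two-sided around a target study day: ±30 days at Day 92, ±14 at Day 394 and ±7 at every other scheduled visit. It cites the protocol's separate Day 92 windows by phase and then overrides them: "For consistency across studies, the same time window will be applied for all studies". It closes with: "Only assessments that fit within the protocol defined visit windows will be used in the analysis of efficacy and immunogenicity for PP analysis set". SAP 5.2 defines Day 1 as the date of the first dose. SAP 6.5 sends the selection of participants for PP immunogenicity analyses at each timepoint to Section 5.5.

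The protocol differs in three ways.

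- **Direction and width.** Appendix 1 gives +2 days at Days 29, 57 and 120, and +14 at Day 394. At Day 92 it gives +30 for Phases 1 and 3b; for the others, "For participants in Phase 2 and Phase 3a, the visit window at Day 92 is +14 days".
- **Minimum intervals.** Section 4.5.3.4: "The Follow-up visit on Day 57 must occur at least 28 days after the second vaccination". For Phase 2/3a, Section 4.5.3.2 adds that "the 3rd vaccination with study vaccine must be at least 56 days (+30 days) after the second vaccination series".
- **Anchor.** When a vaccination is delayed for a listed reason, Section 5.2.1 says "subsequent study visits will be based on calendar days after the receipt of the study vaccine".

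**The concern.** The closing sentence of SAP 5.5 and the list above it cannot both be followed. A programmer who codes the list applies windows that the protocol does not contain. One who codes the sentence leaves the list without a function.

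This matters because Section 5.5 is the only explicit check on when blood was drawn. The deviations that SAP 4.1 lists as grounds for exclusion from the PP immunogenicity sets cover wrong or missed vaccine, non-study vaccine, confounding medication and infection, but not timing. The PP definition does require doses to fall within the protocol window, but that does not reach an early blood draw after a correctly timed dose. The protocol's immunogenicity analysis set (IAS, Section 8.2) excluded data affected by draw-timing deviations; the SAP's version of that set no longer carries the clause.

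Day 57 is the primary immunogenicity timepoint of Phase 1/2/3a, and Day 120 is the readout after the third dose. At stake is whether the PP results at those two timepoints describe samples taken at the intended interval after a dose.

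**Working it through.** **Inputs.** Nominal dosing is Days 1, 29 and 92. SAP windows are from SAP 5.5. Protocol windows are from Appendix 1 and minimum intervals from Protocol 4.5.3.2 and 4.5.3.4.

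**The plan's own day arithmetic.** SAP 6.4 gives Day 36 as 29 + 7 and Day 92 as 29 + 63; both reproduce. The nominal sampling intervals are 57 − 29 = 28 days after dose 2 and 120 − 92 = 28 days after dose 3.

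**Windows side by side** (SAP = target ± window; protocol = target to target + window, nominal dosing):

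| Visit | SAP 5.5 | Protocol |
|---|---|---|
| Day 29 | 22-36 | 29-31 |
| Day 57 | 50-64 | 57-59 |
| Day 92, Phase 2/3a | 62-122 | 92-106 |
| Day 92, Phase 1/3b | 62-122 | 92-122 |
| Day 120 | 113-127 | 120-122 |
| Day 394 | 380-408 | 394-408 |

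**Early side, Day 57.** The SAP window opens on Day 50.

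- Dose 2 on Day 29: 50 − 29 = 21 days, against a minimum of 28. The earliest allowed day is 29 + 28 = 57, so Days 50-56 (7 days) pass although they are too early.
- Dose 2 on Day 31, the end of its +2 window: 50 − 31 = 19 days. The earliest allowed day is 59, so Days 50-58 (9 days) pass although they are too early.

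**Late side, Day 120 (Phase 2/3a), if study days run from Day 1.** The SAP window closes on Day 127. A sample 28 days after dose 3 fits only if dose 3 was given by 127 − 28 = Day 99.

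- Appendix 1 permits the third dose on Days 92-106, which is 15 days. Doses on Days 100-106 (7 of those days) give samples on Days 128-134, all outside the window.
- If the sample is taken at the end of its own +2 window, 30 days after dose 3, the last dose day that fits is 127 − 30 = 97. Then 9 of the 15 days are lost.
- If the limit is read from Protocol 4.5.3.2 as 56 to 86 days after a Day 29 dose 2, the third dose may fall on Days 85-115 (31 days). Doses on Days 100-115 (16 days) lose their 28-day sample.
- On the SAP's own Day 92 upper limit (Day 122), 23 of the 31 days from Day 92 lose it.

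**Late side, if windows are counted from the actual third dose.** The sample is due 28 to 30 days after dose 3, which is Days 120-122 for a Day 92 dose and Days 134-136 for a Day 106 dose. No on-schedule sample is lost.

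**Disclosure.** SAP 5.5 admits to one common Day 92 window across phases. Neither the added minus side nor the change from +2 to ±7 appears in SAP Section 7, where SAP 2.1 says changes are documented.

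**The case against.** The strongest reply is that analysis windows may reasonably be wider than site-scheduling windows, that PP results are only sensitivity or supportive, and that SAP 5.5 is open about the common Day 92 window. All of that stands. It does not explain why the wider windows are called the protocol's, or why a draw that the protocol forbids should count as per protocol.

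The Day 120 loss can also be contested. SAP 5.5 does not state its anchor. SAP 6.4 counts days from the actual second dose, and Protocol 5.2.1 counts visits from the actual dose after a delay. If the target day moves with the dose, nothing is lost. The study-day wording and the Day 1 definition favour the fixed reading but do not settle it.

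Several stronger readings are tempting and are not supported:

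- **Draws from Day 62 breach the 56-day minimum.** That minimum governs the third vaccination, not a blood sample, and the PP requirement on dose timing partly covers an early third dose.
- **The +30 and +14 limits for Phase 2/3a contradict each other.** One is a dose interval (Days 85-115 for a Day 29 dose 2) and the other a visit window (Days 92-106). The second lies inside the first, so both can be met. They still differ: a third dose on Days 107-115 meets one and not the other.
- **The Day 92 and Day 120 windows overlap and so misassign samples.** They overlap on Days 113-122, but they apply to named visits, and SAP 5.2 keeps unscheduled results out of tables.
- **PP is the only robustness check.** The SAP also plans a second seroconversion definition, a supportive binding assay and subgroup analyses.

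**Conclusion.** The rule in SAP 5.5 is wrong as written. Its windows are not the protocol's, and most of the departure is undisclosed.

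The early-draw problem follows directly from the listed windows: with dose 2 on Day 29, seven calendar days of inadmissible Day 57 draws would pass. The documents do not report that any such draw occurred.

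The Day 120 loss is conditional on study days running from Day 1. On that reading, 7 of the 15 third-dose days permitted by Appendix 1 lead to the loss of a sample taken 28 days later. A reader might turn this into 47% of samples lost. The documents give no distribution of dosing days, so 7/15 is a share of calendar days, neither an estimate nor an upper bound for participants.

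The effect stays within the PP analyses. The primary efficacy and immunogenicity analyses use the modified intent-to-treat set and the IAS, which do not depend on Section 5.5. The Day 394 window has no immunogenicity consequence, because those samples were not analyzed (SAP 7.1).

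**What to change.** In SAP 5.5:

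- State the anchor. Derive PP sample windows from the actual date of the preceding dose: Day 57 from dose 2 and Day 120 from dose 3.
- Enforce the protocol's 28-day minimum for the Day 57 draw.
- Either adopt the protocol's one-sided windows, or stop calling the wider ones protocol defined and enter them in Section 7 with a reason.

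The sponsor should also reconcile the Phase 2/3a third-dose limits in Protocol 4.5.3.2 and Appendix 1, so that being within window has one meaning when the PP sets are built.

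The cost is a few lines of SAP text, one revised window derivation and a rerun of the PP tables. No data collection changes.

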## 6 STATISTICAL METHODS

### 6.1 Sample Size Justification

The sample size for the study overall is driven by the sum of the sample size assumptions for the individual phases of the study, as outlined in the subsections below.

#### Sample Size for Phase 1/2/3a Substudy

Data from Phases 1, 2 and 3a will be pooled up to Day 92 for safety analyses, which will be performed in the Phase 1/2/3a SAS and Phase 1/2/3a RAS. The total sample size for Phase 1/2/3a is primarily driven by the size of safety database required at the time of potential EUA application. With approximately 750 participants randomized in Phases 1, 2 and 3a to receive ARCT-154 for the Phase 1/2/3a primary safety analysis, if the incidence rate of an adverse event is 1.0%, the probability to detect one event in 750 vaccinated participants is >99%, based upon the following formula:

$$p = 1 - (1 - R)^N$$

where R = incidence rate and N = sample size

Data from Phases 1, 2 and 3a will be pooled up to Day 92 for immunogenicity analyses, which will be performed in the Phase 1/2/3a IAS. The primary immunogenicity endpoint is defined as the proportion of participants in each study vaccine group that demonstrate seroconversion (defined as: 4-fold increase in titer from baseline) by surrogate virus NAb assay at Day 57.

The null hypothesis is  $H_0^{\text{Immunogenicity}}$ : lower bound 95% CI for  $SC^{154} \leq SC^{\text{Placebo}}$ . A sample size of 750 and 250 participants in the ARCT-154 and placebo groups respectively will provide greater than 90% power to exclude the null hypothesis with a 1-sided type 1 error rate of 0.025 assuming that 10% of participants are excluded from the analysis (for example due to baseline seropositivity), and that  $SC^{154} > 50\%$  and  $SC^{\text{Placebo}} \leq 10\%$ . However, a more conservative hypothesis testing has been added (refer to section 6.2.3 for more details).

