8.4 Statistical Hypothesis

8.4.1 Phase 1/2/3a Substudy Statistical Hypothesis

For the seroconversion rate primary immunogenicity objective, the null hypothesis ($H_0^{\text{Immunogenicity}}$) is that the lower bound of the 95% CI for ARCT-154 seroconversion rate (SC^{154}) is \leq seroconversion rate for placebo (SC^{Placebo}); i.e., $H_0^{\text{Immunogenicity}}$: lower bound 95% CI for $SC^{154} \leq SC^{\text{Placebo}}$. Hence the Phase 1/2/3a part of the study will be considered to meet the primary immunogenicity objective if the lower bound of the 95%CI for $SC^{154} > SC^{\text{Placebo}}$.

There is no hypothesis testing for safety data analysis. Where statistical methods are applied, the emphasis will be on estimation with 95% CIs.

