## 6.2.3 Statistical Hypothesis

### Phase 1/2/3a Substudy Statistical Hypothesis

As per protocol, the primary immunogenicity objective (assessment of ARCT NAb responses by surrogate virus neutralization test (sVNT) at Day 57 versus Placebo) was to be assessed by means of the following Hypotheses:

- Null hypothesis ( $H_0^{\text{Immunogenicity}}$ ): lower bound of the 95% CI of ARCT-154 seroconversion rate at Day 57 ( $SC^{154}$ )  $\leq$  Placebo seroconversion rate at Day 57 ( $SC^{\text{Placebo}}$ ); i.e.,  $H_0^{\text{Immunogenicity}}$ : lower bound 95% CI for  $SC^{154} \leq SC^{\text{Placebo}}$  versus,
- Alternative hypothesis ( $H_1^{\text{Immunogenicity}}$ ): lower bound of the 95% CI of  $SC^{154} > SC^{\text{Placebo}}$

Phase 1/2/3a part of the study was to be considered to meet its primary immunogenicity objective if the lower bound of the 95%CI for  $SC^{154} > SC^{\text{Placebo}}$ . Following regulatory interactions, a more conservative methodology has been added:

- $H_0^{\text{Immunogenicity}}$ : lower bound of the 95% CI of  $(SC^{154}-SC^{\text{Placebo}}) \leq 0\%$  , versus
- $H_1^{\text{Immunogenicity}}$ : lower bound of the 95% CI of  $(SC^{154}-SC^{\text{Placebo}}) > 0\%$

The 95% CI for the difference of seroconversion rates at Day 57 between the two groups (ARCT-Placebo) will be calculated using the Miettinen and Nurminen method. Two-sided  $\alpha = 0.05$  will be used for all tests

There is no hypothesis testing for safety data analysis. Where statistical methods are applied, the emphasis will be on estimation with 95% CIs.

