### 6.5.2 Neutralizing antibody (NAb) responses to ARCT-154 by surrogate virus neutralization test (sVNT)

Neutralizing antibody (NAb) responses by surrogate virus neutralization test (sVNT) as performed by National Institute of Hygiene and Epidemiology, Department of Virology, Vietnam (NIHE), evaluated at Day 1 (baseline) and Day 57 for assessment of seroconversion (based on seroconversion FDA definition provided in section 6.5) in all participants in the Phase 1/2/3a IAS is considered as the Phase 1/2/3a Substudy Primary Immunogenicity Objective (Primary Immunogenicity estimand as described in appendix 9.2). The hypotheses to be tested are described in section 6.2.3.

The number and proportion (and its 95% CI) of participants achieving seroconversion at Day 57 will be provided for each treatment. The two-sided 95% CI of the seroconversion rate will be calculated using the Clopper-Pearson method. In addition, the treatmentdifference, ARCT-154-Placebo, in proportion of participants achieving seroconversion at Day 57 will be provided, along with corresponding two-sided 95% CI (calculated using the Miettinen and Nurminen method)

The following formula, which is provided in the assay kit by the manufacture, will be used for converting sVNT NAb titer (U/mL) to standard unit (IU/mL):

$$\text{Result (IU/mL)} = \text{Result (NAb titer)} / 12.3$$

Neutralizing antibody (Nab) responses by sVNT as performed by NIHE will also be evaluated by GMC, GMFR (not applicable for Day 1), and seroconversion rate (not applicable for Day 1) for the following analysis sets and timepoints where applicable:

- Phase 1 IAS: Day 1, Day 29, Day 57, Day 92.
- Phase 1/2/3a IAS: Day 1, Day 29, Day 57, Day 92 (Phase 1/2/3a Substudy Secondary Immunogenicity Objective)
- Phase 2/3a IAS: Day 1, Day 29, Day 57, Day 92, Day 120 (Phase 1/2/3a Substudy Exploratory Immunogenicity Objective)

Neutralizing antibody (Nab) responses by sVNT, as performed by PPD Laboratories, USA, (Angiotensin-converting enzyme 2 (ACE2)/sVNT) will be evaluated by GMC, GMFR, and seroconversion rate for the following analysis sets and timepoints where applicable:

- Phase 1 IAS: Day 1, Day 57.
- Phase 1/2 IAS: Day 1, Day 57 (Phase 1/2/3a Substudy Exploratory Immunogenicity Objective)

Supportive analyses will be performed in the corresponding per protocol (PP) immunogenicity sets. Subgroup analyses will be performed as described in section 6.5.7.

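### The 0.025 type I error in the Phase 1/2/3a sample-size text belongs to the added difference rule, not to the protocol rule it is attached to (16–19%), and the SAP does not name the deciding rule

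*SAP*

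**What the plan says.** Protocol 8.4.1 says the substudy "will be considered to meet the primary immunogenicity objective if the lower bound of the 95%CI for" the ARCT-154 seroconversion rate is above the placebo rate. Section 8.7.1.1 repeats the rule. The synopsis and section 8.5.1 give the matching null hypothesis with a sample-size statement, which SAP 6.1 carries over. On size and power, SAP 6.1 reads: "A sample size of 750 and 250 participants in the ARCT-154 and placebo groups respectively will provide greater than 90% power". The error rate tied to that power follows in these words: "to exclude the null hypothesis with a 1-sided type 1 error rate of 0.025". The calculation allows for a tenth of participants dropping out of the analysis and takes an ARCT-154 rate above 50% and a placebo rate no higher than 10%. SAP 6.1 then closes with a sentence noting that a more conservative test has been added and referring to 6.2.3.

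SAP 6.2.3 reports the protocol rule in the past tense ("Phase 1/2/3a part of the study was to be considered to meet its primary immunogenicity objective if the lower bound of the 95%CI for" the ARCT-154 rate exceeded the placebo rate). It continues: "Following regulatory interactions, a more conservative methodology has been added". The added rule requires the lower 95% limit for the difference, ARCT-154 minus placebo, to exceed 0%, using the Miettinen-Nurminen method. The change table in SAP 7.1 also calls this an addition. SAP 6.5.2 plans both a Clopper-Pearson interval for each arm and a Miettinen-Nurminen interval for the difference. On the decision it says only: "The hypotheses to be tested are described in section 6.2.3". That section holds both pairs of hypotheses.

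**The concern.** The protocol rule compares a confidence limit from one arm with a point estimate from the other. No external value for the placebo rate is given, so the placebo figure is the rate observed in about 225 people, and it is treated as if known. With 3:1 allocation, placebo is the smaller arm and contributes most of the variance of the difference, all of which the rule leaves out. The 0.025 is therefore not a property of the rule it is attached to.

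What is at stake is the stated error rate of a primary decision rule in a substudy whose data were intended for an emergency use application, and clarity about which of two rules decides. A reader of SAP 6.1 alone would take 0.025 to describe the protocol rule.

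**Working it through.** **Inputs.** SAP 6.1: 750 and 250 randomized, 10% excluded, so 750 × 0.9 = 675 and 250 × 0.9 = 225 evaluable; rates 50% and 10%; one-sided error 0.025; power above 90%. SAP 6.5.2: Clopper-Pearson for a single arm, Miettinen-Nurminen for the difference. The common true rate under the null is not given, so a range of 2% to 50% is shown.

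**The plan's own figures.** Power reproduces: at 50% versus 10% it is above 99.9% under either rule. The 0.025 is recovered only if the placebo rate is a known constant. Against a fixed 10% with n = 675, the Clopper-Pearson lower limit first exceeds 10% at 84 responders, and the exact error is 0.0226.

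**Normal approximation for the protocol rule.** With a common rate p:

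- variance of the ARCT-154 rate: p(1−p)/675
- variance of the difference: p(1−p)(1/675 + 1/225) = 4p(1−p)/675
- placebo share of that variance: (1/225)/(4/675) = 75%
- the standard error of the difference is therefore twice that of the ARCT-154 rate

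The rule is met when the observed difference exceeds 1.96 ARCT-154 standard errors, which is 1.96/2 = 0.98 standard errors of the difference. P(Z > 0.98) = 0.164.

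**Exact check.** All outcomes at 675:225 were enumerated from the two binomial distributions, with equal true rates:

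| Common rate | Protocol rule (Clopper-Pearson) | Difference rule (Miettinen-Nurminen) |
|---|---|---|
| 2% | 0.194 | 0.015 |
| 5% | 0.177 | 0.020 |
| 10% | 0.170 | 0.022 |
| 20% | 0.165 | 0.023 |
| 30% | 0.163 | 0.024 |
| 50% | 0.163 | 0.026 |

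One million simulated trials at 10% gave 0.169 for the protocol rule. Other single-arm intervals do not rescue the figure: at 10%, Wald gives 0.158 and Wilson 0.183. Without the 10% exclusions (750:250) the Clopper-Pearson error at 10% is 0.169.

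**How the two rules relate.** At 675:225 the difference rule is met in 67,388 outcomes, and every one of them also meets the protocol rule. The added rule is strictly nested in the old one. So:

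- if the difference rule decides, or if both are required, the error is that of the right-hand column;
- if either suffices, the error is that of the left-hand column.

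**Chance that the rules disagree.** At 50% versus 10% it is about 1e-26. At 50% versus 30% it is about 0.0003.

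**The case against.** The strongest reply is that the SAP has already dealt with this. The paragraph in 6.1 that carries the 0.025 ends by pointing to the stricter test, 6.2.3 writes the protocol rule as history, 7.1 lists the change against Protocol 8.4.1, and 6.5.2 plans the Miettinen-Nurminen interval. In addition, the rules practically never disagree at the assumed rates. SAP 6.2.4 disclaims any procedure for controlling type I error across this substudy's endpoints, the sample size is said to be driven mainly by the safety database, and by SAP 2.5 the primary immunogenicity analysis had already been performed.

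Most of this stands, and it limits the practical weight. It also answers a stronger reading that a reader might infer, namely that the current SAP runs this objective at a 16% error rate. The documents do not support that. It would require that meeting either rule is enough, which no section says. Because the added rule is nested in the old one, adding it as an alternative could never alter a result, and calling it more conservative would then make no sense.

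The reply does not make the 0.025 correct. SAP 6.1 still states the old null hypothesis in the present tense with that figure attached. Every mention of the new rule says it was added, none that it replaces the old one, and 6.5.2 refers to a section containing both. Having no multiplicity procedure is a separate matter from misstating the error of a single test.

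**Conclusion.** Wrong as written on the stated error rate, with low practical impact. The protocol rule has a one-sided error of about 16% to 19% for common rates of 50% down to 2%, not 0.025. This assumes 675:225 evaluable, Clopper-Pearson limits, and the observed placebo rate as comparator. The added Miettinen-Nurminen rule has an error of about 0.015 to 0.026 over the same range and is the rule that the 0.025 describes. The SAP points towards it without naming it as the deciding rule.

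It would be wrong to conclude that the immunogenicity result is in doubt or the sample too small: power exceeds 99.9% at 50% versus 10% under either rule. The Phase 3b efficacy test does not depend on this substudy's rule.

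**What to change.** In SAP 6.1 and 6.2.3, state that the objective is met only if the lower limit of the Miettinen-Nurminen 95% confidence interval for the ARCT-154 minus placebo seroconversion rate exceeds 0%, and that this replaces the rule in Protocol 8.4.1. In 6.1, move the one-sided 0.025 and the power statement to that rule; the power claim of more than 90% remains true. Record it in SAP 7.1 as a replacement, so that the reference in 6.5.2 leads to a single deciding rule. While the text is open, both pairs of hypotheses could be written about the true rates instead of confidence limits; this is notation only.

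The cost is SAP wording. The interval for the difference is already planned, and neither the sample size, the data nor the conduct of the trial changes.
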